3.4 Statistical Analyses

3.4.1 General Considerations

All statistical analyses will be performed under the responsibility of the Sponsor's Biostatistics Platform using the SAS® software, Version 9.4 or above (SAS Institute, Cary, North Carolina, USA).

For descriptive purposes, the following statistics will be presented:

Disposition and follow- up description	Categorical data	At least number of participants (Percentage of participants are also possible).
	Continuous data	Mean, standard deviation, minimum and maximum.
Baseline	Categorical data	Number of participants.
characteristics		Percentage of participants.
	Continuous data	Mean, standard deviation, quartiles, minimum and maximum.
Clinical safety results	Categorical data	Solicited: Number and percentage (95% confidence intervals [CIs] for main endpoints) of participants.
		Unsolicited: Number and percentage (95% CIs for main endpoints) of participants and number of events.
Immunogenicity results	Categorical data (seroconversion, cutoff)	Number and percentage (95% CIs for main endpoints) of participants.
	Continuous data	Log10: Mean and standard deviation.
	(titer / concentration)	Anti-Log10 (work on Log10 distribution, and anti- Log10 applied): Geometric mean, 95% CI of the geometric mean, quartiles, minimum, and maximum. Graphical representation by Reverse Cumulative
		Distribution Curve (RCDC).

Table 3.1: Descriptive statistics produced

The CI for the single proportion will be calculated using the exact binomial method (Clopper-Pearson method, quoted by Newcombe (1) ie, using the inverse of the beta integral with SAS®.

For immunogenicity results, assuming that log_{10} transformation of the titers / data follows a normal distribution, at first, the mean and the 95% CI will be calculated on log_{10} (titers / data) using the usual calculation for normal distribution (using Student's t distribution with n-1 degree of freedom), then antilog transformations will be applied to the results of calculations, in order to provide geometric means (GMs) and their 95% CI.

Confidential/Proprietary Information Page 18 of 40 For each participant, randomized study group will be assigned from the randomization number assigned to the participant, and injected vaccine/study group will be derived from the label of the vaccine(s) injected on D01, as collected in the CRF.

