3.3 Populations for Analyses

For the purposes of analysis, the following analysis sets will be defined:

Participant Analysis Set	Description
Randomized	All participants randomized by study IRT to one of the study groups.
Safety Analysis Set (SafAS)	Participants who have received at least one dose of the study vaccine. All participants will have their safety analyzed after each dose according to the vaccine they actually received, and after any dose according to the vaccine received at the 1st dose.
	Safety data recorded for a vaccine received out of the protocol design will be excluded from the analysis (and listed separately).
Full analysis set (FAS)	Subset of randomized participants who received at least 1 dose of the study vaccine and had a post-vaccination blood sample. For the assessment of the immune response by SN assay, the analysis will be performed on the participants from FAS who were randomized in the exploratory subset (FAS-SN).
	Participants will be analyzed according to the intervention to which they were randomized.
Per-protocol analysis set (PPAS)	Subset of the FAS. Participants presenting with at least one of the following criteria will be excluded from the PPAS:
	Participant did not meet all protocol-specified inclusion criteria or met at least one of the protocol-specified exclusion criteria
	Participant did not complete the vaccination schedule
	Participant received a vaccine other than the one that he / she was randomized to receive
	Preparation and / or administration of vaccine was not done as per-protocol
	Participant did not receive vaccine in the proper time window
	Participant did not provide the post-dose serology sample at visit 2 or at visit 3 in the proper time window ([D26, D39] or VAC2+[D26, D39] respectively) or a post-dose serology sample was not drawn at visit 2 or visit 3
	Participant received protocol-prohibited medications impacting or that may have an impact on the immune response, as specified in the database following data review of concomitant medications.
	Any other deviation identified during the study conduct and identified as relevant by the clinical team during data review, ie, indicated as excluding participants from this analysis set in the manual deviations dataset.

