3.4.2 Primary Endpoints

The immunogenicity parameters will be calculated in each study group with their 95% CIs using the exact binomial distribution (Clopper-Pearson method) for proportions and using normal approximation of log-transformed for GMTs.

Statistical Methodology for analyzing the primary 8 endpoints (GMTs and SC rates).

Non-inferiority of RIV4 as compared to IIV4 in participants 3 to 8 years of age will be conducted for GMTs and SC rates.

For each strain, the NI methodology will be applied to compare the post-vaccination GMTs and the SC rates between the groups using a 1-sided Type I error rate of 0.025 with the given individual hypothesis.

The primary analysis will be conducted into 2 steps starting with testing for NI of GMTs between RIV4 and IIV4. If NI of GMTs based on the 4 strains is demonstrated, then NI for SC will be also tested.

Step1: Geometric Mean Titers

Assuming that log10 transformation of the data follows a normal distribution, the log10 (data) will be used for the statistical analysis, then antilog transformations will be applied to the results of calculations, in order to provide the results in terms of geometric means (GMs).

The statistical methodology is based on a 2-sided 95% CI of the ratio of the GMTs (RIV4 divided by IIV4) at 28 days after the last vaccination. Non inferiority for GMTs is demonstrated if the lower limit of the 2-sided 95% CI of the GMT ratio is > 0.667 for each of the 4 virus strains.

As appropriate according to the number of participants in the respective subgroups, ANCOVA will be conducted for each strain with a model including the terms log10 of HAI titer at D01, priming status, age subgroup, season and the treatment represented by the vaccine administered as independent factors, and log10 HAI titer of each virus strain separately of the last vaccination as a response variable. ANCOVA will be conducted using Proc Mixed in SAS (all terms in the model are fixed). In Proc Mixed, the "Estimate" statement will allow to derive the difference (RIV4 minus IIV4) of the Least Squares-means and the 95% CI in their original log10 values. By exponentiating the difference (RIV4 minus IIV4) and its 95% CI; the 95% CI of ratio (RIV4/IIV4) will be obtained and be used to derive GMTs NI final results.

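### The SAP reads the vaccine received from the D01 label only, which conflicts with its own rule that safety after each dose follows the vaccine given at that dose

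*SAP*

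**What the plan says.** SAP 3.4.1 (General Considerations) assigns each participant a randomized group from the randomization number and an injected group from the first-day label: "injected vaccine/study group will be derived from the label of the vaccine(s) injected on D01, as collected in the CRF". The SAP gives no other derivation of the vaccine received.

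SAP 3.3 (Populations for Analyses), matching Protocol 9.3, sets two rules for the Safety Analysis Set:

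- Per-dose safety: "All participants will have their safety analyzed after each dose according to the vaccine they actually received".
- Any-dose safety: "after any dose according to the vaccine received at the 1st dose".

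The same table excludes a child from the Per-Protocol Analysis Set (PPAS) on any of several criteria. Three bear on this point. The first is the wrong-vaccine criterion: "Participant received a vaccine other than the one that he / she was randomized to receive". The second concerns how the dose was prepared or given: "Preparation and / or administration of vaccine was not done as per-protocol". The third is any relevant deviation "indicated as excluding participants from this analysis set in the manual deviations dataset". For the Full Analysis Set (FAS): "Participants will be analyzed according to the intervention to which they were randomized".

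Previously unvaccinated children receive two doses 28 days apart, the second at Visit 2 (Protocol Table 1.2, SAP Table 1.3). Protocol Table 6.2 plans 353 such children per arm.

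**The concern.** The two safety rules in SAP 3.3 differ only when a child's two doses differ, so the authors evidently foresaw that case. The derivation in 3.4.1 supplies the value for the any-dose rule and nothing for the per-dose rule at dose 2. If it is used for both, it returns the wrong vaccine in exactly the children for whom the rules were separated.

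What is at stake is the secondary safety objective. In SAP Table 2.1, immediate events, solicited reactions, unsolicited events and medically attended events are all defined by vaccination. The interim safety summaries by vaccine group in SAP 3.5.1 could inherit the same misassignment.

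**Working it through.** **1. Follow one child through the rules.** Take a two-dose child randomized to RIV4, given RIV4 on D01 and, by mistake, IIV4 at Visit 2. The 3.4.1 variable equals RIV4.

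| Analysis | What SAP 3.3 requires | What the D01 variable gives | Agree? |
|---|---|---|---|
| Safety after dose 1 | RIV4 | RIV4 | Yes |
| Safety after any dose | RIV4 (dose-1 convention) | RIV4 | Yes |
| Safety after dose 2 | IIV4 | RIV4 | **No** |
| PPAS | Child excluded | Not named in the criterion | No conflict in the text |
| FAS | RIV4, as randomized | Not used | No conflict |

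Only the post-dose-2 safety row fails. It fails in the same way if the error was at dose 1 and dose 2 was as randomized, because the variable carries the D01 value forward.

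**2. How many children.**

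- Two-dose children: 353 + 353 = 706, and 706/1412 = 50%.
- The documents give no mix-up rate. Assumed rates at dose 2: 706 × 0.005 = 3.5, about 4; 706 × 0.01 = 7.1, about 7. At less plausible rates of 2% and 5% the counts are about 14 and 35.
- Effect on a safety percentage: if all 7 errors fell in one arm, 7/353 = 2.0%. A post-dose-2 percentage in that arm could then be off by at most about 2 percentage points, and only if the misassigned children differed completely from the rest.

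**3. Primary analysis with such children excluded, as the PPAS text requires.** First the plan's own power, with n = 600 per arm and one-sided alpha 0.025:

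- GMT, per strain: Φ(0.1759 / (0.6 × √(2/600)) − 1.96) = 99.9%, where 0.1759 = −log10(0.667). To the fourth power this is 99.6%, as stated in SAP 3.2.
- Seroconversion, per strain: Φ(0.10 / √(2p(1−p)/600) − 1.96) = 93.4% at p = 0.5 and 96.6% at p = 0.7 (stated: 93.7% and 96.7%). Product over the four strains: 81.3% (stated: 82.0%).
- Overall: 99.6% × 81.3% = 81.0% (stated: 82.0%). The 1-point gap is of no consequence here.

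Two-dose children are half of each arm, so a mix-up rate r removes a fraction r/2. At 0.5%, n = 600 × 0.9975 = 598.5 and power is 80.8%. At 1%, n = 600 × 0.995 = 597 and power is 80.7%.

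**4. What if such children were wrongly kept in the PPAS?** Assume the worst: equal swaps in both arms, each swapped child responding wholly like the other arm, and the true difference at the margin m. The observed difference shrinks to m(1 − r), and the one-sided error per test is Φ(m·r/SE − 1.96). At r = 0.5% this is 0.026 to 0.027, and at 1% it is 0.027 to 0.028, against 0.025.

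**The case against.** The strongest reply is that SAP 3.3 already states the safety rule. The per-dose sentence is specific, and 3.4.1 does not say that its one-value-per-participant variable replaces it. On that view only a derivation line is missing. The data also exist: vaccination is recorded in the CRF at both VAC1 and VAC2 (Protocol Table 1.2), and syringe treatment numbers serve to record what was administered (Protocol 6.3.2). The Safety Analysis Set further provides that data for a vaccine given outside the protocol design are excluded and listed. If that covers a swap between the two study vaccines, the events would be set aside and not misassigned.

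Most of this is fair, and it is why the consequence is conditional. But the only stated derivation names D01, so a programmer following 3.4.1 gets a value that 3.3 contradicts. Whether the out-of-design sentence covers a swap between study vaccines is left open, and applying it at dose 2 needs dose-level information in any case.

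A reader might infer more: that the per-protocol rule misses a dose-2 mix-up, so the child stays in the primary analysis. The documents do not support this. The wrong-vaccine criterion names neither a dose nor the 3.4.1 variable, and the administration and manual-deviation criteria are two further routes to exclusion. Comparing the randomized and injected groups of 3.4.1 would be an easy way to program the criterion, and it would miss the error, but the SAP does not prescribe it.

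A reader might also infer a general attribution to the wrong arm. That goes too far: the FAS is analyzed as randomized, and any-dose safety uses dose 1 by design. The ANCOVA term in SAP 3.4.2 ("the treatment represented by the vaccine administered as independent factors") does not change this for the PPAS. Once wrong-vaccine children are excluded, administered and randomized vaccine coincide there.

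**Conclusion.** The inconsistency is real but minor. SAP 3.4.1 and the per-dose safety rule in SAP 3.3 cannot both be followed after dose 2 when a child's two vaccines differ. The effect is confined to descriptive post-dose-2 safety, for about 4 to 7 of 706 children if mix-ups occur in 0.5% to 1%; that rate is an assumption. The primary non-inferiority conclusion does not change under the PPAS as written. Excluding these children costs 0.2 to 0.3 points of power, and even retaining them by a programming slip would barely move the type I error at those rates.

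**What to change.** Replace the D01-only derivation in SAP 3.4.1 with text to this effect:

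- The vaccine received is derived separately for each vaccination from the label recorded in the CRF at that visit.
- The dose-specific value is used for per-dose safety.
- The D01 value is kept for any-dose safety.
- The PPAS wrong-vaccine criterion is checked at every dose the child received, not through the D01 variable.

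It would help to add whether the Safety Analysis Set sentence on vaccines outside the protocol design applies to a swap between the two study vaccines.

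The cost is a few sentences and one derived variable per dose. No new data should be needed, assuming the label is captured at Visit 2 as it is at D01. Protocol 9.4 provides for amending the SAP before any database lock, so the edit fits the existing process.

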3.4.2 Primary Endpoints

The immunogenicity parameters will be calculated in each study group with their 95% CIs using the exact binomial distribution (Clopper-Pearson method) for proportions and using normal approximation of log-transformed for GMTs.

Statistical Methodology for analyzing the primary 8 endpoints (GMTs and SC rates).

Non-inferiority of RIV4 as compared to IIV4 in participants 3 to 8 years of age will be conducted for GMTs and SC rates.

For each strain, the NI methodology will be applied to compare the post-vaccination GMTs and the SC rates between the groups using a 1-sided Type I error rate of 0.025 with the given individual hypothesis.

The primary analysis will be conducted into 2 steps starting with testing for NI of GMTs between RIV4 and IIV4. If NI of GMTs based on the 4 strains is demonstrated, then NI for SC will be also tested.

Step1: Geometric Mean Titers

Assuming that log10 transformation of the data follows a normal distribution, the log10 (data) will be used for the statistical analysis, then antilog transformations will be applied to the results of calculations, in order to provide the results in terms of geometric means (GMs).

The statistical methodology is based on a 2-sided 95% CI of the ratio of the GMTs (RIV4 divided by IIV4) at 28 days after the last vaccination. Non inferiority for GMTs is demonstrated if the lower limit of the 2-sided 95% CI of the GMT ratio is > 0.667 for each of the 4 virus strains.

As appropriate according to the number of participants in the respective subgroups, ANCOVA will be conducted for each strain with a model including the terms log10 of HAI titer at D01, priming status, age subgroup, season and the treatment represented by the vaccine administered as independent factors, and log10 HAI titer of each virus strain separately of the last vaccination as a response variable. ANCOVA will be conducted using Proc Mixed in SAS (all terms in the model are fixed). In Proc Mixed, the "Estimate" statement will allow to derive the difference (RIV4 minus IIV4) of the Least Squares-means and the 95% CI in their original log10 values. By exponentiating the difference (RIV4 minus IIV4) and its 95% CI; the 95% CI of ratio (RIV4/IIV4) will be obtained and be used to derive GMTs NI final results.

In the interim analysis, the statistical methodology will be based on a 2-sided 95% CI of the ratio of the GMTs (RIV4 divided by IIV4) at 28 after the last vaccination. NI for GMTs will be demonstrated if the lower limit of the 2-sided 95% CI of the GMT ratio is > 0.667 for each of the 4 virus strains. The 95% CI will be calculated using normal approximation of log-transformed titers. The Per-Protocol Analysis Set (PPAS) will be used as the primary analysis set.

Confidential/Proprietary Information Page 19 of 40

Step 2: Seroconversion rates

The statistical methodology is based on a 2-sided 95% CI of the difference in SC rates (RIV4 minus IIV4) at 28 days after last vaccination. NI for SC rates is demonstrated if the lower limit of the 2-sided 95% CI is > -10% for the 4 strains. The 95% CI of the rate difference is computed using the Wilson Score method without continuity correction.

As a sensitivity analysis, a generalized linear model (binomial-identity model) based on a link function named "identity link" will be used. The regression coefficient for the treatment (vaccines administered) in the binomial-identity model represent the proportions difference (difference between RIV4 and IIV4). The model will include priming status, age subgroup, season, and the treatment term (represented by the vaccines administered) as independent factors. The difference (RIV4 – IIV4) and its 95% CI obtained will be used to derive the SC NI results.

In the sensitivity analysis, the statistical methodology will be based on a 2-sided 95% CI of the difference in SC rates (RIV4 – IIV4) at 28 days after last vaccination. The NI for SC rates will be demonstrated if the lower limit of the 2-sided 95% CI is > -10% for the 4 strains.

In the interim analysis, no sensitivity analysis will be conducted for SC due to the limited number of participants included in the interim analysis.

Non-inferiority will be assessed on PPAS as the main analysis set and will be confirmed on the FAS.

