6.3 Measures to Minimize Bias: Randomization and Blinding

6.3.1 Randomization and Allocation Procedures

On the day of enrollment, participants aged 3 to 8 years who meet all the inclusion criteria but none of the exclusion criteria and sign the assent form (according to local regulations) and whose parent(s)/legally acceptable representative sign the ICF will be randomized in a 1:1 ratio, stratified by season, site, age subgroup and by vaccination status for influenza, such as each study randomized vaccine group will have approximately 50% of participants aged 3 to 5 years and 50% of participants aged 6 to 8 years, to receive either RIV4 or IIV4. Age subgroup will be stratified by vaccination status for influenza, such as each age subgroup will have approximately 50% of participants previously vaccinated against influenza and 50% of participants previously unvaccinated against influenza. Participants will receive either 1 or 2 doses 28 days apart depending on whether they were previously vaccinated against influenza, respectively (see Table 6.2).

RIV4 (N=706)		IIV4 (N=706)				Total (N=1 412)		
against i	vaccinated nfluenza ose	influ	ted against	against i	vaccinated nfluenza ose	unvaccina influ	ously ted against enza days apart	
Approxi mately 50% aged 3 to 5 years	Approxi mately 50% aged 6 to 8 years	Approxi mately 50% aged 3 to 5 years	Approxi mately 50% aged 6 to 8 years	Approxi mately 50% aged 3 to 5 years	Approxi mately 50% aged 6 to 8 years	Approxi mately 50% aged 3 to 5 years	Approxi mately 50% aged 6 to 8 years	
353 353		353 353			1412			

Table 6.2: Participants disposition by group

In addition, at least 400 participants per vaccine group will be randomized to be part of the subset population to assess the immunogenicity based on the SN method. Subset randomization will be stratified by vaccination status against influenza subgroup and age subgroups (3 to 5 years and 6 to 8 years) in order to have approximately 25% of subset participants in each stratum (see Table 6.3).

RIV4			IIV4				Total	
(N=400)			(N=400)				(N=800)	
against i	vaccinated nfluenza ose	Previously unvaccinated against influenza 2 doses 28 days apart		Previously vaccinated against influenza 1 dose		Previously unvaccinated against influenza 2 dose 28 days apart		

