The primary analysis will be conducted into 2 steps starting with testing for NI of GMTs between RIV4 and IIV4. If NI of GMTs based on the 4 strains is demonstrated, then NI for SC will be also tested.

Step 1: Geometric Mean Titers

Assuming that log10 transformation of the data follows a normal distribution, the log10 (data) will be used for the statistical analysis, then antilog transformations will be applied to the results of calculations, in order to provide the results in terms of geometric means (GMs).

The statistical methodology is based on a 2-sided 95% CI of the ratio of the GMTs (RIV4 divided by IIV4) at 28 days after the last vaccination. Non inferiority for GMTs is demonstrated if the lower limit of the 2-sided 95% CI of the GMT ratio is > 0.667 for each of the 4 virus strains.

ANCOVA will be conducted for each strain with a model including the terms log10 of HAI titer at D01, priming status, age subgroup, season and the treatment represented by the vaccine administered as independent factors, and log10 HAI titer of each virus strain separately of the last vaccination as a response variable. ANCOVA will be conducted using Proc Mixed in SAS (all terms in the model are fixed). In Proc Mixed, the "Estimate" statement will allow to derive the difference (RIV4 minus IIV4) of the Least Squares-means and the 95% CI in their original log10 values. By exponentiating the difference (RIV4 minus IIV4) and its 95% CI; the 95% CI of ratio (RIV4/IIV4) will be obtained and be used to derive GMTs NI final results.

Step 2: Seroconversion

The statistical methodology will be based on a 2-sided 95% CI of the difference in SC rates (RIV – IIV4) 28 days after the final vaccination. Non-inferiority for SC will be demonstrated if the lower limit of the 2-sided 95% CI is > -10% for the 4 strains. The 95% CI of the rate difference will be computed using the Wilson Score method without continuity correction

Non-inferiority will be assessed on PPAS as the main analysis set and will be confirmed on the FAS.

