3.2 Sample Size Determination

A total of approximately 1200 evaluable participants 3 to 8 years of age will be assessed (approximately 50% participants enrolled in the age group 3-5 years and 50% participants enrolled in the age group 6-8 years) in this study. Approximately 50% of participants enrolled within age group will be primed, and the other 50% will be unprimed.

Assuming similar GMTs in both groups and a standard deviation of log titers of 0.6 with a NI margin of 1.5 (or 1/1.5 = 0.667); NI for GMTs would be demonstrated with a power of approximately 99.6%.

Assuming in each vaccine group the same expected SC rates (0.5, 0.5, 0.7, 0.7) for each of the 4 strains (A/H1N1, A/H3N2, B/Yamagata and B/Victoria), based on conservative estimates from historical data, and a NI margin of 10%, the NI for SC can be demonstrated with a statistical power of approximately 82.0% (93.7%, 93.7%, 96.7% and 96.7% for each strain, respectively).

Hence, the overall study power is estimated to be approximately 82.0% (82.0% = 99.6%[GMTs] x 82.0%[SC]).

As shown above, to keep the study power above 80%, the sample size was increased accordingly, to have an overall Type II error <20% for the 8 NI tests.

Assuming 15% attrition rate in this age group; a total of approximately 1412 participants 3 to 8 years of age will be enrolled in this study.

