3.4.3 Secondary Endpoints

Immunogenicity

The immunogenicity parameters will be calculated with their 95% CIs using the exact binomial distribution (Clopper-Pearson method) for proportions and using normal approximation of log-transformed for GMTs and GMTs ratio. The 95% CI of proportions difference (ie, difference between vaccine groups in SC) will be calculated using Wilson Score method without continuity correction. All analyses will be conducted by study group.

In particular, the following descriptive statistics will be displayed:

- GMTs of individual HAI titer on D01 and 28 days after the last vaccination (D29 or D57)
- Percentage of participants with detectable HAI titer, ie, with a titer ≥ 10 (1/dil) at D01 and 28 days after the last vaccination (D29 or D57)
- GMs of Individual HAI titer ratio: 28 days after the last vaccination (D29 or D57) / D01
- SC rates (titer < 10 [1/dil] at D01 and post-injection titer ≥ 40 [1/dil] at D29 or D57, or titer ≥ 10 [1/dil] at D01 and a ≥ 4-fold-rise in titer [1/dil] at D29 or D57)
- Percentage of participants with titers ≥ 40 (1/dil) on D01 and 28 days after the last vaccination (D29 or D57)

• The RCDCs of pre-vaccination titer prior to the first vaccination (D01), and post-vaccination titer at D29 after last vaccination will be generated for each study group. The RCDCs will include the plots of the 2 study groups the same figure.

The analysis will be conducted for each immunogenicity variable on the PPAS, and on FAS if the attrition rate from FAS to PPAS is greater than 10%.

In addition, subgroup analysis will be performed; in particular, immunogenicity will be described according to season, sex, race, previous influenza vaccination status (received a seasonal influenza vaccine in the last past influenza season or not), baseline seropositivity status (seropositive and seronegative are defined as baseline antibody titer $\geq 1:10$ or < 1:10), and age subgroups (3 to 5 and 6 to 8 years) as appropriate according to number of participants in the respective subgroups. Subgroup analyses will be performed on PPAS.

Safety

For the main safety parameters, 95% CIs of point estimates will be calculated using exact binomial method (Clopper-Pearson method) for single proportions and using the normal approximation for quantitative data.

All analyses will be descriptive; no hypotheses will be tested.

The number of participants with documented safety will be used as denominator of the frequencies.

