	 For each vaccine group and each strain, calculate the proportion P_{RIV4} and the proportion P_{IIV4} corresponding the SC rates use the predictive distribution of these parameters to derive B times datasets (e.g. 100.000) of the participants not yet enrolled in the study (to reach the approximately 1200 planned PPAS subjects overall in both vaccines) – with a seed value in SAS of 1545313 (for RIV4) and 4878646 (for IIV4)
3	Combine the interim datasets and the B datasets of the after interim to constitute the final and complete B datasets using the same sequence number. The final complete B datasets will be used to deriving the 2-sided 95% CI of the difference between SC of each antigen for each one of the B complete datasets.
4	Use the 2-sided 95% CI of the difference (between SC of RIV4 and SC of IIV4) for each B dataset to calculate the PPoS by deriving the proportion of datasets with the NI success.
	NI success in each complete dataset will be determined by comparing the lower bound of the 95% CI to the NI margin

Table 3.4: Description and Definition of the Main Steps in Calculating PPoS for NI Based on SC rates for each Vaccine Strain, Separately

The age of subjects was stratified into 2 strata, planning to reach approximately 50% of subjects of age 2 to 5 years, and approximately 50% of subjects of age 6 to 8 years.

Each age subgroup was stratified into 2 strata, planning to reach approximately 50% of subjects primed, and approximately 50% of subjects who are unprimed.

Confidential/Proprietary Information Page 28 of 40

VV-CLIN-0628295 5.0

Hence, 4 subsets (2 age subgroup times 2 vaccination status) of subjects were formed. Each subset should include approximately 25% of subjects to be vaccinated in this study.

If the distribution of the study subsets in the interim PPAS dataset is substantially different from what was planned in the protocol, which is approximately 25% of subjects in each subset, a complementary calculation of PPOS may be performed, thus running the above steps 1 and 2 in each of the 4 subsets to reach 300 PPAS subjects overall in each subset (age subgroup and vaccination status), and adding an extra step 2bis, concatenating the 4 strata within each of the B datasets, before performing step 3 and step 4.

3.5.2.2 Overall PPoS of the 4 GMTs, and overall PPoS of the 4 SCs, and Study overall PPoS (4 GMTs and 4 SC rates)

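### The primary seroconversion interval ignores the age and vaccination-status strata used in randomization; a stratified Newcombe-Wilson interval would be a low-cost efficiency gain, not the repair of an error

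*SAP*

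**What the plan says.** **Randomization.** Under protocol 6.3.1, participants "will be randomized in a 1:1 ratio, stratified by season, site, age subgroup and by vaccination status for influenza". Protocol Table 4.1 also names site, age and vaccination status; SAP Table 1.1 names age group and vaccination status only. Age and vaccination status are common to all three.

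**GMT step.** Protocol 9.4.2 and SAP 3.4.2 use an ANCOVA with baseline titer, priming status, age subgroup and season. The SAP makes this subject to adequate subgroup numbers.

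**SC step.** The SAP states: "The 95% CI of the rate difference is computed using the Wilson Score method without continuity correction". Protocol 9.4.2, Step 2, agrees: "The 95% CI of the rate difference will be computed using the Wilson Score method without continuity correction". Neither stratifies. Non-inferiority requires the lower limit to exceed -10% for all four strains.

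**Adjustment for SC.** This appears only in a binomial-identity sensitivity model with the same -10% rule: "The model will include priming status, age subgroup, season, and the treatment term (represented by the vaccines administered) as independent factors". It is dropped at the interim: "In the interim analysis, no sensitivity analysis will be conducted for SC due to the limited number of participants included in the interim analysis".

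**Power.** SAP 3.2 gives 82.0% for the four SC tests (93.7%, 93.7%, 96.7%, 96.7% per strain) and 99.6% for the GMTs.

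**The concern.** The two primary steps treat the same strata differently, and the unadjusted step is the one that limits power. A pooled interval uses the total binomial variance in each arm. Stratified randomization has already largely balanced the part of that variance that lies between strata, so the pooled interval is wider than it needs to be when strata differ. At stake is power above the plan's 80% target on the limiting step, in a trial where one failed strain is enough to miss the primary objective. The target itself is not at risk.

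**Working it through.** **Inputs.** From SAP 3.2: 600 evaluable per arm, SC rates 0.5/0.5/0.7/0.7 equal in both arms, margin 10 points, 15% attrition. From SAP 3.1: one-sided 0.025. From protocol 6.3.1: four age-by-priming strata of about equal size. Assumed: an SC gap of 0 to 40 points between two halves of the strata, the same in both arms. As in the SAP, strains are multiplied as independent.

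**1. The plan's own figure.** Exact enumeration of the pooled Newcombe-Wilson lower limit, 600 per arm, gives 93.70% at 0.5 and 96.66% at 0.7. Jointly, 0.9370² × 0.9666² = 0.820. The stated 82.0% is reproduced.

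**2. Why a gap matters.** For a 50:50 split with gap d, the within-stratum variance is p(1-p) - d²/4. At p = 0.5 and d = 0.40 this is 0.25 - 0.04 = 0.21, which is 84% of the variance the pooled interval uses.

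**3. Error rate of the pooled interval.** At a true difference of -10 points (0.4 vs 0.5) and a 40-point gap:
- SE used: √((0.24 + 0.25)/600) = 0.0286
- Actual SD: √((0.20 + 0.21)/600) = 0.0261
- Effective critical value: 1.96 × 0.0286/0.0261 ≈ 2.14, so one-sided error is about 1.6%

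Exact enumeration gives 2.55% at no gap, 2.31% at 20 points, 2.03% at 30 and 1.64% at 40. With random 15% attrition the 40-point figure is 1.7-1.8%.

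**4. Stratified Newcombe-Wilson interval.** For stratum k and arm i:
- Weights: w_k proportional to n1k·n0k/(n1k + n0k), summing to 1
- Arm rate: P_i = Σ w_k p_ik; difference: P_1 - P_0
- V_ik = p_ik(1 - p_ik)/n_ik
- z_i = 1.96 × √(Σ w_k² V_ik) / Σ w_k √V_ik
- L_i and U_i: w_k-weighted sums of the stratum Wilson limits computed with z_i
- Lower limit: (P_1 - P_0) - √((P_1 - L_1)² + (U_0 - P_0)²)

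**5. Joint SC power, same gap in all four strains, no true vaccine difference.** Simulated with 150 per arm per stratum. The pooled column agrees with exact enumeration to about 0.1 point.

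| Gap (points) | Pooled | Stratified | Gain |
|---|---|---|---|
| 0 | 81.9% | 82.0% | 0.1 |
| 10 | 82.3% | 82.5% | 0.2 |
| 20 | 83.2% | 84.6% | 1.4 |
| 30 | 84.9% | 87.6% | 2.7 |
| 40 | 87.0% | 91.3% | 4.3 |

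With random 15% attrition from 176-177 per arm per stratum, pooled versus stratified power is 81.8 vs 81.9% at no gap, 82.8 vs 84.5% at 20, 84.2 vs 87.6% at 30 and 86.0 vs 91.3% at 40. One-sided error of the stratified interval is about 2.6% throughout.

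**6. Age instead of priming.** With no priming gap and an age gap of 20 or 30 points, the result is the same: 83.2 vs 84.6% and 84.9 vs 87.6%.

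**7. Gap in only two strains** (one at 0.5, one at 0.7). The gain roughly halves. At 40 points:
- Stratified: 0.9671 × 0.9882 × 0.9368 × 0.9673 = 0.866
- Pooled: 0.9524 × 0.9794 × 0.9368 × 0.9669 = 0.845

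**The case against.** The strongest reply is that nothing is broken. The hypothesis concerns the pooled difference, the sample size assumes one rate per strain and arm, and the quoted powers are exactly those of the pooled interval. Hypothesis, sample size and test therefore match. Any departure from nominal error is in the safe direction for non-inferiority, and adjusted SC results are already planned as a sensitivity analysis. The gain rests on gaps the documents do not give, and changing a primary test after a first season has been enrolled is not trivial. All of this stands, and it makes the change optional. It does not remove the gain, because the limiting step leaves the design's strata unused while the GMT step uses them.

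A reader might go further in four ways that the documents do not support:
- **That the pooled test is invalid or the SC step underpowered.** Under the planned overall rates, its power is 82.0% and rises with a gap.
- **That a gain is assured because primed and unprimed children must differ.** No stratum-specific SC rates are stated, so neither the size nor the direction of a gap is known.
- **That stratifying costs power unless the gap exceeds some threshold.** That holds for a Wald-type Mantel-Haenszel interval, which loses about 0.2-0.5 points at no gap. The stratified Newcombe-Wilson form shows no material loss.
- **That the existing sensitivity model could simply be made primary.** Having main effects only, it weights strata by inverse variance, so its estimate can leave the pooled difference when the vaccine difference varies by stratum. In an assumed case (overall rate 0.7; -15 points in low-SC strata, -5 in high-SC strata, pooled -10), simulated one-sided error was about 5%, 8% and 14% at gaps of 20, 30 and 40 points.

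**Conclusion.** The point holds as an efficiency improvement. The pooled interval is sound and meets the plan's power target with or without a stratum gap. Stratifying costs essentially nothing if strata do not differ. If all four strains share a gap, it adds about 1.4-1.7, 2.7-3.4 and 4.3-5.3 points of joint SC power at 20, 30 and 40 points; if only two do, about half of that. These are scenarios, not bounds. They assume the planned overall rates, equal-sized strata, independent strains, the same gap in both arms and no true vaccine difference. Keeping the pooled interval is acceptable.

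**What to change.** In protocol 9.4.2 and SAP 3.4.2, make the primary SC interval the stratified Newcombe-Wilson interval set out above: no continuity correction, Mantel-Haenszel weights over age subgroup by priming status, non-inferiority if the lower limit exceeds -10%. Keep the pooled Wilson interval as a sensitivity analysis.

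- **Strata.** Use priming status as randomized, not the SAP 3.4.3 subgroup variable, which depends on vaccination in the last season only. Leave season out until the three descriptions of the randomization strata are reconciled.
- **Interim.** SAP Table 3.4, step 2, simulates one proportion per arm. Using the new interval there needs the stratum-wise simulation, with stratum labels kept; at present "a complementary calculation of PPOS may be performed" only if the subset mix is substantially off plan. Otherwise, state that the SC predictive power uses the pooled interval.
- **Timing.** Protocol 9.4 provides for amending the SAP before any database lock. Blinded staff should decide and document the change before the interim lock. The documents do not show whether that lock has passed; if it has, leave the primary test as it is.
- **Cost.** A protocol and SAP amendment with any approval it needs, minor programming, and one-sided error at about the nominal level (2.6%) where the pooled interval would have been conservative.
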